6.1.1.2 Dose Administration and Schedule in the Long-term Treatment Period

Subjects will continue to receive their assigned blinded dose of investigational product (placebo or efavaleukin alfa) beginning at the week 12 visit. The exception will be placebo nonresponder subjects, who are defined as those randomized to placebo during the induction period and failed to achieve clinical response at week 12. These placebo nonresponder subjects will be assigned in a blinded manner to receive [REDACTED] µg [REDACTED] dose during the long-term treatment period (Table 6-1). For the purposes of treatment assignment into the long-term treatment period, clinical response is defined as a decrease from baseline in the modified Mayo score (using the endoscopic subscore assigned by the investigator) of ≥ 2 points and at least 30% reduction from baseline, and a decrease in the rectal bleeding subscore of ≥ 1 or an absolute rectal bleeding subscore of 0 or 1.

Table 6-1. Investigational Product Administration: Long-term Treatment Period

Investigational Product Administration	
Induction Period	Long-term treatment period

Day 1 to Week 12	Week 12 up to Week 52 or Early Termination
Placebo [redacted] responder ^{a, d}	Placebo [redacted]
Placebo [redacted] nonresponder ^{b, d}	[redacted] µg [redacted]
[redacted] µg [redacted] d	[redacted] µg [redacted]
[redacted] µg [redacted] d	[redacted] µg [redacted]
[redacted] µg [redacted] d	[redacted] µg [redacted]

^a A placebo responder subject is one who achieved clinical response at week 12.

^b A placebo nonresponder subject is one who did not achieve clinical response at week 12.

^c Subjects randomized to efavaleukin alfa will remain on the same dose through the long-term treatment period and includes responders and nonresponders.

^d Clinical response for the purpose of treatment assignment in the exploratory long-term treatment period will be assessed using the modified Mayo score and the endoscopic subscore assigned by the investigator.

Subjects who were nonresponders at week 12, and who have an inadequate response by week [redacted] will be discontinued from further investigational product administration in long-term treatment period (Section 4.1.2).

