8.4.4.3 Follow-up of Adverse Events and Serious Adverse Events

After the initial adverse event/serious adverse event report, the investigator is required to proactively follow each subject at subsequent visits/contacts. All adverse events and serious adverse events will be followed until resolution, stabilization, until the event is otherwise explained, or the subject is lost to follow-up (as defined in Section 7.3). Further information on follow-up procedures is given in Section 11.4.

All new information for previously reported serious adverse events must be sent to Amgen immediately and no later than 24 hours following awareness of the new information. If specifically requested, the investigator may need to provide additional follow-up information, such as discharge summaries, medical records, or extracts from the medical records. Information provided about the serious adverse event must be consistent with that recorded on the Events eCRF.

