- When an adverse event or serious adverse event occurs, it is the responsibility of the investigator to review all documentation (eg, hospital progress notes, laboratory, and diagnostics reports) related to the event.
- The investigator will then record all relevant adverse event/serious adverse event information in the Event case report form (CRF).
- The investigator must assign the following mandatory adverse event attributes:
 - Adverse event diagnosis or syndrome(s), if known (if not known, signs or symptoms);
 - Dates of onset and resolution (if resolved);
 - Did the event start prior to first dose of investigational product;
 - Assessment of seriousness;
 - Severity (or toxicity defined below);
 - Assessment of relatedness to investigational product (efavaleukin alfa/placebo), other noninvestigational product(s)/auxiliary medicinal product(s), devices, and/or study-required activity and/or procedures;
 - Action taken; and
 - Outcome of event.
- If the severity of an adverse event changes from the date of onset to the date of resolution, record as a single event with the worst severity on the Event electronic CRF.
- It is not acceptable for the investigator to send photocopies of the subject's medical records to sponsor/responsible contract research organization (CRO) in lieu of completion of the Event eCRF page.
- If specifically requested, the investigator may need to provide additional follow-up information, such as discharge summaries, medical records, or extracts from the medical records. In this case, all subject identifiers, with the exception of the subject number, will be blinded on the copies of the medical records before submission to Amgen.
- The investigator will attempt to establish a diagnosis of the event based on signs, symptoms, and/or other clinical information. In such cases, the diagnosis (not the

individual signs/symptoms) will be documented as the adverse event/serious adverse event.

Evaluating Adverse Events and Serious Adverse Events

Assessment of Severity

The investigator will make an assessment of severity for each adverse event and serious adverse event reported during the study. The assessment of severity will be based on:

The Common Terminology Criteria for Adverse Events, version 5 which is available at the following location:

http://ctep.cancer.gov/protocolDevelopment/electronic_applications/ctc.htm.

Assessment of Causality

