- The investigator is obligated to perform or arrange for the conduct of supplemental measurements and/or evaluations as medically indicated or as requested by Amgen to elucidate the nature and/or causality of the adverse event or serious adverse event as fully as possible. This may include additional laboratory tests or investigations, histopathological examinations, or consultation with other health care professionals.
- If a subject is permanently withdrawn from protocol-required therapies because of a serious adverse event, this information must be submitted to Amgen.
- If a subject dies during participation in the study or during a recognized follow-up period, the investigator will provide Amgen with a copy of any post-mortem findings including histopathology.
- New or updated information will be recorded in the originally completed Event eCRF.
- The investigator will submit any updated serious adverse event data to Amgen immediately and no later than 24 hours of receipt of the information.

[figure not shown]
Reporting of Serious Adverse Event

Serious Adverse Event Reporting via Electronic Data Collection Tool

- The primary mechanism for reporting serious adverse event will be the electronic data capture (EDC) system.
- If the EDC system is unavailable, then the site will report the information to Amgen using a paper-based Serious Adverse Event Contingency Report Form (also referred to as the electronic Serious Adverse Event [eSAE] Contingency Report Form) (see [REDACTED]) immediately and no later than 24 hours of the investigator's awareness of the event.
- The site will enter the serious adverse event data into the electronic system as soon as it becomes available.
- After the study is completed at a given site, the EDC system will be taken off-line to prevent the entry of new data or changes to existing data.
- If a site receives a report of a new serious adverse event from a study subject or receives updated data on a previously reported serious adverse event after the EDC system has been taken off-line, then the site can report this information on the paper-based Serious Adverse Event Contingency Report Form (see [REDACTED]
[REDACTED])
- Once the study has ended, serious adverse event(s) suspected to be related to investigational product will be reported to Amgen if the investigator becomes aware of a serious adverse event. The investigator should use the paper-based Serious Adverse Event Contingency Report Form to report the event.

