**Treatment-emergent adverse event (TEAE):**

Treatment-emergent adverse events are events categorized as Adverse Events (AEs) starting on or after first dose of IP as determined by “Did event start before first dose of investigational product?” equal to “No” or missing on the Events eCRF and up to the EOS date.

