#### **9.6 Safety Analyses**

##### **9.6.1 Adverse Events**

The Medical Dictionary for Regulatory Activities (MedDRA) version 27.0 or later will be used to code all events categorized as adverse events to a system organ class and a preferred term. The severity of each adverse event will be graded using CTCAE criteria version 5.0 or later ([Appendix A](#)). Summaries of adverse events during the induction adverse event exposure period will be presented by actual treatment received in the induction period. Exposure-adjusted subject incidence rates for the overall study period will be presented by actual treatment received in the overall study.

Subject incidence of all TEAEs, serious TEAEs, TEAEs leading to discontinuation from investigational product, fatal TEAEs, treatment-related TEAEs, treatment-related serious TEAEs, treatment-related TEAEs leading to discontinuation from investigational product,

treatment-related fatal TEAEs, and TEAEs of interest that occur in the induction adverse event exposure period will be summarized.

Subject incidence of treatment-emergent adverse events identified by COVID-19 standardized MedDRA queries and serious adverse events occurring on or after the COVID-19 infection that occur in the induction adverse event exposure period will also be summarized.

Subject incidence of events of interest (standardized MedDRA queries and/or Amgen Medical Queries) that occur in the induction adverse event exposure period will also be summarized according to their categories and preferred term. Events of interest could include but are not limited to Hypersensitivity, Tachyarrhythmias, Tachypnea, Hematopoietic Cytopenia, Drug Reaction with Eosinophilia, Leucocyte Changes, Infection and Infestation, Cytokine Release Syndrome, and Injection Site Reaction. Number of episodes and duration of treatment-emergent injection site reactions will be further summarized by treatment group.

In addition, summaries of TEAEs and serious TEAEs occurring in at least 5% of the subjects in any treatment arm and serious TEAEs occurring in at least 2% of the subjects in any treatment arm by preferred term that occur in the induction adverse event exposure period will be provided in descending order of frequency.

Summaries of TEAEs and serious TEAEs that occur in the induction adverse event exposure period will be tabulated by system organ class, preferred term, and grade. An overall summary of adverse events by toxicity grade will be provided.

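### The induction adverse event tables can show a severity, seriousness or discontinuation first reached after week 12, including worsening on efavaleukin shown under placebo

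*Protocol*

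**What the plan says.** **Recording (Protocol Section 11.4, Appendix 4).** "If the severity of an adverse event changes from the date of onset to the date of resolution", the site must "record as a single event with the worst severity on the Event electronic CRF". Seriousness, action taken and outcome are likewise single attributes of the event. The listed mandatory attributes include onset and resolution dates but no date of a change in grade. The follow-up part of the same appendix adds: "New or updated information will be recorded in the originally completed Event eCRF".

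**Follow-up (Protocol 8.4.4.3).** "All adverse events and serious adverse events will be followed until resolution, stabilization, until the event is otherwise explained", so follow-up can run well past week 12.

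**Selection (SAP 5.1).** TEAEs are "events categorized as Adverse Events (AEs) starting on or after first dose of IP", as determined by the eCRF question "Did event start before first dose of investigational product". The induction adverse event exposure period runs from first dose to the earliest of end of study, day 90, and the later of the week 12 endoscopy date and the day before the week 12 dose.

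**Tabulation (SAP 9.6.1).** TEAEs and serious TEAEs in the induction adverse event "exposure period will be tabulated by system organ class, preferred term, and grade". Serious TEAEs and TEAEs leading to discontinuation of investigational product are summarized for the same window. The column is the treatment actually received in induction, which SAP 5.1 bases on product received up to the end of induction date.

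**Switch (Protocol 6.1.1.2).** Of placebo subjects without clinical response at week 12, the protocol says: "These placebo nonresponder subjects will be assigned in a blinded manner to receive" a dose of efavaleukin in the long-term period.

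**The concern.** The induction window is evidently meant to confine these tables to what happened on induction treatment. The recording rule achieves that for the onset of an event only. Grade, seriousness and action taken come from a record that stays open until the event ends, and treatment can change while it is open.

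Take a placebo subject with a grade 1 event starting in week 10. The subject does not respond, starts efavaleukin at week 12, and the event becomes grade 3 in week 20. Under the written rules this is one event with week 10 onset and grade 3, so it is tabulated as a grade 3 induction event on placebo. No new event is recorded on efavaleukin.

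At stake is the attribution of severity, seriousness and discontinuation in the placebo-controlled induction adverse event tables. These tables inform the safety part of dose evaluation.

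**Working it through.** The documents state no figure to reproduce. The check is a trace of the rules, followed by a scale.

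**1. Can later severity enter an induction row?**
- Span of the recorded grade: onset to resolution, with no cut at week 12 (Appendix 4).
- Selection: TEAE status depends on start. SAP 9.6.1 refers to events occurring in the window without defining the term. Onset is the natural reading given the start-based TEAE definition, and no date of grade change is among the required attributes that would support another.
- Column: treatment received up to the end of induction. Later efavaleukin does not reclassify a placebo subject.
- Neither document asks for the grade at the end of the window, or for a new record when an ongoing event worsens after it.

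So the answer is yes for events unresolved at the end of the window. An event that resolves and recurs would be a new record and is not affected.

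**2. Where does the window end?** With end of study later, the end is min[day 90, max(week 12 dose day − 1, week 12 endoscopy day)].
- Endoscopy day 85, dose day 85: min[90, max(84, 85)] = day 85.
- Endoscopy day 85, dose day 88: min[90, max(87, 85)] = day 87.
- Endoscopy day 90, dose day 93: min[90, max(92, 90)] = day 90.

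The nominal week 52 visit is day 365. An ongoing event therefore has up to about 365 − 85 = 280 days in which to worsen and still set the induction grade.

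**3. Scale per subject.** Planned arm size is 60 (Protocol 4.1.1). One subject is 1/60 = 1.67 points, two are 3.33 and three are 5.0.

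**4. Illustration for placebo switchers.** Only the 60 is from the documents. The assumed ranges are: 50–70% of placebo subjects are nonresponders, 80–90% of these enter long-term treatment, 10–30% of those have an induction-onset event ongoing at week 12, and 5–20% of these worsen later.
- Low: 60 × 0.5 × 0.8 × 0.10 × 0.05 = 0.12 subjects; 0.12/60 = 0.2 points.
- High: 60 × 0.7 × 0.9 × 0.30 × 0.20 = 2.27 subjects; 2.27/60 = 3.8 points.

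This counts any worsening, such as grade 1 to 2; fewer would reach grade 3. It is a gross count in one arm, not a bias in the comparison between arms.

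**5. Do other tables correct it?**
- The overall-study analysis (SAP 5.1 and 9.6.1) gives subjects who went from placebo to efavaleukin their own group, and reports serious and discontinuation events as exposure-adjusted incidence rates. These rates are not described by grade. Exposure runs from first dose to end of study, so a switcher's placebo and efavaleukin time are pooled.
- SAP 9.2 counts discontinuations of investigational product in the induction period, with reasons, by randomized group.
- SAP 9.6.1 also mentions an overall summary by toxicity grade, without stating its period or grouping.

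None of these changes the grade shown in the induction table.

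**The case against.** The strongest reply has four parts.

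- **The practice is ordinary.** One record at worst grade is adequate while treatment stays constant. Here treatment changes mid-event for part of one arm.
- **Much of the information appears elsewhere.** For discontinuation and serious events this stands in part: SAP 9.2 and the separate switcher group limit the harm. It does not stand for the induction grade table.
- **The wording about events occurring in the window could be read more narrowly.** It could, but the required data do not date a grade change, so a stated rule would still be needed.
- **The size is assumed and probably small.** This stands.

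A reader might also infer several stronger things that the documents do not support.

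- *That the tables are biased toward no difference.* Efavaleukin subjects who continue stay on efavaleukin, and their later worsening enters their own columns. Placebo responders stay on placebo. The net direction is not determined.
- *That the primary tables drift between database locks.* SAP 7.2 locks the data supporting the primary analysis. Worsening before that lock can still enter, because the lock waits for the last subject's week 12 while earlier subjects are already in long-term treatment.
- *That pre-dose events are a comparable problem.* Protocol 8.4.4.1 collects non-serious events only after first dose, so this could concern only serious events during screening. The point does not depend on them.
- *That all randomized safety comparisons are affected.* Laboratory and vital-sign summaries do not use the adverse event record.

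**Conclusion.** The point holds as a rule that can attribute severity to the wrong treatment period. Under the written text, an induction-onset event still ongoing at week 12 can be tabulated in induction with a grade, seriousness or discontinuation first reached later. For placebo nonresponders this puts worsening on efavaleukin under placebo.

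The direction of any net bias is uncertain and the effect is probably small. Each affected subject is 1.67 points at the planned 60 per arm. The illustrative 0.12 to 2.27 placebo subjects rest on assumed rates. The conclusion also rests on reading inclusion in the window as onset in the window, which the SAP implies but does not state. It merits a correction because the attribution is wrong by rule and the remedy is cheap.

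**What to change.** In SAP 9.6.1, state that grade, seriousness and action taken in the induction tables are those reached within the induction adverse event exposure period, and that later worsening is reported under the treatment then received. Obtain the date of change by querying only events ongoing at the first long-term dose. If the queries are not feasible, footnote the induction tables and list the induction-onset events ongoing at that dose.

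Keep any-TEAE incidence and the injection site reaction episode counts based on the original single event, so that worsening does not create extra episodes or split durations.

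The cost is a limited set of queries and one SAP paragraph. Induction counts of higher-grade, serious and discontinuation events may fall slightly, as intended. Rewriting the Appendix 4 recording rule is not needed. SAP Section 11 says the trial was terminated after the August 2024 interim, so a change in eCRF recording would come late, whereas the SAP wording and targeted queries may still be practical.

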11.5 Appendix 5. Contraceptive Guidance and Collection of Pregnancy and Lactation Information

Study-specific contraception requirements for females of childbearing potential are outlined in Section 5.2. Contraceptive use and methods should be consistent with local regulations for subjects participating in clinical studies.

Male and female subjects of childbearing potential should be advised of the pregnancy prevention requirements and the potential risk to the fetus if they become pregnant or father a child during treatment and for 6 weeks after the last dose of investigational product.

Definition of Females of Childbearing Potential

A female is considered fertile following menarche and until becoming post-menopausal unless permanently sterile. Permanent sterilization methods include documented hysterectomy, bilateral salpingectomy, and bilateral oophorectomy. Females with documented permanent infertility due to an alternate medical cause (eg, Mullerian agenesis, androgen insensitivity, gonadal dysgenesis), can be considered not of childbearing potential.

Note: Bilateral tubal ligation/occlusion is not considered a permanent sterilization method.

Note: Documentation from the following sources is acceptable to provide confirmation of each sterilization method: 1) review of subject's medical records; 2) subject's medical examination; or 3) subject's medical history interview.

A postmenopausal female is defined as:

- A woman of ≥ 55 years with no menses for 12 months without an alternative medical cause OR
- A woman age < 55 years with no menses for at least 12 months and with a follicle-stimulating hormone (FSH) level within the definition of "postmenopausal range" for the laboratory involved. In the absence of 12 months of amenorrhea, confirmation with more than one FSH measurement is required.

Contraception Methods for Female Subjects

Highly Effective Contraceptive Methods

- Combined (estrogen and progestogen containing) hormonal contraception associated with inhibition of ovulation (oral, intravaginal, or transdermal)
- Progestogen-only hormonal contraception associated with inhibition of ovulation (oral, injectable, implantable) (except in Japan)
- Intrauterine device
- Intrauterine hormonal-releasing system

- Bilateral tubal ligation/occlusion
- Vasectomized partner (provided that partner is the sole sexual partner of the female subject of childbearing potential and that the vasectomized partner has received medical assessment of the surgical success)
- Sexual abstinence (defined as refraining from heterosexual intercourse during the entire period of risk associated with the study treatments; the reliability of sexual abstinence must be evaluated in relation to the duration of the trial and the preferred and usual lifestyle of the subject)

Collection of Pregnancy Information

Female Subjects Who Become Pregnant

[figure not shown]
- Investigator will collect pregnancy information on any female subject who becomes pregnant while taking investigational product(s) and/or non-investigational product(s)/auxiliary medicinal product(s) through 6 weeks after last dose of investigational product.
- Information will be recorded on the Pregnancy Notification Form (see [REDACTED] The form must be submitted to Amgen Global Patient Safety immediately and no later than 24 hours of the site's awareness of a subject's pregnancy. (Note: Sites are not required to provide any information on the Pregnancy Notification Form that violates the country or regions local privacy laws).
- After obtaining the female subject's signed consent for release of pregnancy and infant health information, the investigator will collect pregnancy and infant health information and complete the pregnancy questionnaire for any female subject who becomes pregnant while taking investigational product(s) and/or non-investigational product(s)/auxiliary medicinal product(s) through 6 weeks after the last dose of investigational product. This information will be forwarded to Amgen Global Patient Safety. Generally, infant follow-up will be conducted up to 12 months after the birth of the child (if applicable).
- Any termination of pregnancy will be reported to Amgen Global Patient Safety, regardless of fetal status (presence or absence of anomalies) or indication for procedure.
- While pregnancy itself is not considered to be an adverse event or serious adverse event, any pregnancy complication or elective termination of a pregnancy for medical reasons will be reported as an adverse event or serious adverse event. Abnormal pregnancy outcomes (eg, spontaneous abortions, stillbirth, fetal death, congenital anomalies) will be reported as an adverse event or serious adverse event. Note that an elective termination with no information on a fetal congenital malformation or maternal complication is generally not considered an adverse event, but still must be reported to Amgen as a pregnancy exposure case.
- Any serious adverse event occurring as a result of a post-study pregnancy which is considered reasonably related to the study treatment by the investigator, will be reported to Amgen Global Patient Safety as described in Section 11.4. While the investigator is not obligated to actively seek this information in former study subjects, he or she may learn of a serious adverse event through spontaneous reporting.
- Any female subject who becomes pregnant while participating will discontinue investigational product while pregnant (see Section 7.1 for details).

[figure not shown]
Male Subjects with Partners Who Become Pregnant or Were Pregnant at the Time of Enrollment

- In the event a male subject fathers a child during treatment, and for an additional 6 weeks after discontinuing investigational product(s) and/or noninvestigational product(s)/auxiliary medicinal product(s), the information will be recorded on the Pregnancy Notification Form. The form (see [REDACTED]) must be submitted to Amgen Global Patient Safety immediately and no later than 24 hours of the site's awareness of the pregnancy. (Note: Sites are not required to provide any information on the Pregnancy Notification Form that violates the country or regions local privacy laws).
- The investigator will attempt to obtain a signed consent for release of pregnancy and infant health information directly from the pregnant female partner to obtain additional pregnancy information.
- After obtaining the female partner's signed consent for release of pregnancy and infant health information, the investigator will collect pregnancy outcome and infant health information on the pregnant partner and her baby and complete the pregnancy questionnaires. This information will be forwarded to Amgen Global Patient Safety.
- Generally, infant follow-up will be conducted up to 12 months after the birth of the child (if applicable).
- Any termination of the pregnancy will be reported to Amgen Global Patient Safety regardless of fetal status (presence or absence of anomalies) or indication for procedure.

Collection of Lactation Information

- Investigator will collect lactation information on any female subject who breastfeeds while taking investigational product(s) and/or noninvestigational product(s)/auxiliary medicinal product(s) through 6 weeks after the last dose of investigational product.
- Information will be recorded on the Lactation Notification Form (see below) and submitted to Amgen Global Patient Safety immediately and no later than 24 hours of the investigator's awareness of the event.
- Study treatment will be discontinued if female subject breastfeeds during the study as described in exclusion criterion 230.
- With the female subjects signed consent for release of mother and infant health information, the investigator will collect mother and infant health information and complete the lactation questionnaire on any female subject who breastfeeds while taking investigational product(s) and/or non-investigational product(s)/auxiliary medicinal product(s) through 6 weeks after discontinuing investigational product(s) and/or non-investigational product(s)/auxiliary medicinal product(s).

